#### **8.2.4.3 DNA Methylation**

To better define the sensitivity of vaginal DNA methylation in the detection of endometrial cancer, an additional experiment whereby vaginal DNA extracted through tampon collection will be evaluated for hypermethylation. DNA from the corresponding endometrial tumor (low grade endometrial carcinoma or CAH/EIN) will be separately analyzed and the tumor DNA-vaginal DNA pairs will be analyzed for concordance of methylation across 850,000 CpG sites. Vaginal DNA will be extracted per methods already described for the genomics portion of this study from the cell pellets. The same DNA extracted from the cell pellet will be used for NGS. A bisulfite conversion step will be performed as part of the standard Illumina Methylation array protocol, which requires 250 ng minimum DNA input. Vaginal and tumor DNA methylation studies will be performed using the EPIC methylation chip (Illumina Inc.), which evaluates methylation in 850,000 CpG sites that include both promoter and enhancer elements using 500 ng of DNA.

The proposed experimental design will accomplish several novel goals. First, this design will establish the global methylation pattern of each patient's endometrial carcinoma/EIN which can be statistically compared to the primary study endpoint (Ki-67 response to exemestane treatment) in the context of potentially clinically relevant methylation groups established by the TCGA. Second, the design will allow to rigorously test the sensitivity/limit of detection for specific methylation pattern discrimination in the tampon DNA for underlying carcinoma. Finally, the design will allow for a robust comparison of clinical utility between ultra-sensitive DNA sequencing, methylation analysis, and proteomics to determine which platform is most sensitive for detection of disease.

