**For E.O. Ospedalli Galliera (EOG) site only**, participants will be approached to participate prior to their actual diagnosis of CAH/EIN/low grade endometrial cancer. Standard of care in this region includes a visit with a gynecologic oncologist and subsequent hysteroscopy with biopsies when patients have postmenopausal bleeding and a high suspicion for pre-invasive or invasive disease. Therefore, the research team will meet the potential participants for a prescreening visit before the diagnostic hysteroscopy. Patients will sign a pre-screening consent on this day before the procedure. During the examination, the surgeon will perform one diagnostic biopsy and one research only biopsy. If CAH/EIN/low grade EC is confirmed then participants will sign the main study consent. If the patient does not meet the CAH/EIN/low grade EC diagnosis the research tissue samples will be destroyed. On the day before the baseline (pre-surgical) clinic visit the team will obtain written consent for study participation. A tampon will be placed by a study nurse. Lab tests for eligibility will be collected. Eligibility documents will be submitted to CLO for verification. On the day of the pre-surgical clinic visit, the study nurse will remove the tampon and place in cold PBS. The study drug will be dispensed to the participant at this visit after receiving the eligibility confirmation from CLO. If the lab test results are not within study required parameters, the patient will be deemed ineligible and the tampon will be removed and discarded during this clinic visit.

Participants who meet eligibility requirements will begin oral exemestane daily for at least 21 days (no longer than 42 days) with a dose of 25 mg/day by mouth (PO) until the day prior to surgery.

The day the participant begins taking exemestane is considered Day 1 of the study. The study team will make telephone contacts to the participants on

- Day 0/1 as a reminder to start exemestane
- Day 15 ( $\pm 2$  days) to assess for adverse events and other symptoms, and review medication changes.

- One day prior to surgery to assess for adverse events and other symptoms and review medications. In addition, the participants will be reminded to insert a tampon 8-12 hours before surgery.

Participants will be encouraged to contact the investigator or study coordinator with any new symptoms or concerns at any time during the trial.

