#### **4. PARTICIPANT SELECTION**

In the U.S. based sites, whenever feasible, potential participants will be pre-screened for the study and contacted by the study team prior to their planned baseline (pre-surgical) clinic visit. The advantage of this is to introduce the study concept to the potential participant and allow her to place a tampon for specimen collection prior to her baseline (pre-surgical) clinic visit. If the participant gives verbal consent over the phone for the screening portion of the study, a pre-study packet will be mailed to her. This packet will

contain an informed consent form for her review and 2 commercially available tampons (one to be inserted in her vagina 8-12 hours before her baseline (pre-surgical) clinic visit and one for back up) along with instructions on how to insert a tampon (Appendix D). The tampon will be removed during the baseline (pre-surgical) clinic visit by the physician at the time of the pelvic exam. If the participant is eligible and agrees to take part in the study, the tampon will be processed and the resultant protein and DNA will serve as a pre-treatment sample. If the participant is either not eligible or refuses to sign the study consent, the tampon will be discarded. If a subject was unable to place a tampon prior to their baseline (pre-surgical) clinic visit, she will still be eligible for participation in this study.

**For EOG site only**, the patient will be approached for study participation when they first present with postmenopausal bleeding.

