#### **4.1 Inclusion Criteria**

Eligible participants must meet the following requirements:

4.1.1 Females with a histologically proven CAH/ EIN or low grade (grade 1 or grade 2) endometrial carcinoma (EC) for which surgery is planned. The pathologic report from the referring facility will be used to determine pathologic eligibility. This report must be within 45 days of their baseline (pre-surgical) clinic visit.

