#### **8.2.5 Protein markers via tampon recovery before and after treatment:**

We propose a proteomic analysis of vaginal specimens and endometrial biopsies as an exploratory experiment to determine if response to exemestane correlates with a change in vaginal and endometrial proteins. Proteins identified in this experiment could potentially serve as surrogate biomarkers for exemestane response. We also anticipate discovering a different protein profile in the tampon collected proteins and tissue biopsies of women with CAH/EIN vs. low grade endometrial cancer.

[name] has successfully performed proteomic studies using the Olink platform on serum protein from healthy women and women with ovarian cancer. The methodology that [name] optimized in her preliminary studies will be applied to this study. The concentration of protein in each sample will be determined by using the bicinchoninic acid (BCA) assay. If necessary due to low protein yields in the tampon washings, they will be passed through an Amicon filter (3 kD cut-off) in order to concentrate the proteins. In preliminary studies, the total amount of protein in each 1 mL of tampon washing sample ranged from 65 to 500 ug (i.e. enough for multiple proteomic analyses). We also plan to extract protein from the

cell pellet that is saved from the tampon washing (described in 8.2.6.1) and from tumor biopsies (pre- and post-treatment with exemestane).

For the proteomic pilot studies, we will analyze samples from the first 10 patients that will be sent directly to the University of Minnesota. In particular, we will be analyzing 4 samples from each patient: (i) the PBS tampon washing pre-treatment, (ii) the cell pellet from the tampon washing pre-treatment, (iii) the PBS tampon washing post-treatment with exemestane, and (iv) the cell pellet from the tampon washing post-treatment with exemestane.

The rationale for using the PBS rinse of the tampon as well as the cell pellet from the tampon is four-fold.

1. The PBS rinse from the tampon is a rich source of protein that contains proteins that are secreted from the uterus (and endometrium), cervix, and vagina by the patient over the time period that the tampon was placed in her vagina. These proteins will be absorbed by the tampon (along with blood proteins and cells that are shed). In our previous studies, we found a sufficient amount of protein in the PBS rinse to perform protein based assays. .

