pellets). We will provide these samples to the University of Minnesota Genomics Center, whose staff will run the samples as a fee-for-service. 1- send Olink ~50 ug of protein from the 40 tampon washing samples (10 pre-surgery supernatant, 10 post-surgery supernatant, 10 pre-surgery cell pellets, and 10 post-surgery cell pellets). 2- Once optimal dilutions have been determined, we will be able to test the other 4 Olink panels that are relevant to this study as a fee-for-service.

SomaLogic technology was also initially designed to quantify the levels of proteins in sera and/or plasma. However, SomaLogic uses technology based on aptamers to quantify protein levels in many types of samples (See their website at <https://somalogic.com/>). Their technology allows for the quantification of 7000 proteins simultaneously from 75 ul of protein at 0.2 ug/ul.

We propose to: 1- Send SomaLogic ~10 ug of protein from the 40 tampon washing samples (10 pre-treatment supernatants, 10 post-treatment supernatants, 10 pre-treatment cell pellets, and 10 post-treatment cell pellets). 2- As a fee-for-service, have SomaLogic run the 40 samples on their SomaScan platform.

Once we have the data back from Olink and SomaLogic, we will be able to analyze the data to identify proteins that are differentially expressed between the tampon supernatants and cell pellet lysates, the pre- and post-treatment samples from the same patient, as well as those proteins that are differentially expressed between the women whose tumors respond to Exemestane treatment and those whose tumors do not respond.

Since the Olink and SomaLogic platforms are not compatible with denatured proteins, it will not be possible to use either platform to analyze the protein extracts from the biopsies (which were extracted in AllPrep reagent for recovery of DNA and protein) or tumor tissues. The tissue sample extracts can be used for other protein experiments, such as validation of the proteins identified in the tampon washing samples by Western immunoblotting.

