##### **10.1.1 Tissue samples**

Endometrial biopsy tissue sample at baseline (pre-surgical) clinic visit

- First pass will immediately go into formalin and within 24 hours a Formalin Fixed Paraffin Embedded (FFPE) block will be made. Blocks will be shipped on frozen ice packs to prevent melting of the FFPE block.
- Second pass will be placed in a stabilizing agent (AllProtect) and stored at 4°C and then shipped on frozen ice packs.

Hysterectomy Tumor tissue sample at surgery

- Section snap-frozen and stored at -70/-80°C. Remove up to 1x1x1 cm of tumor and cut in half. If there is not a visible lesion, select a random 1x1x1 cm area from the endometrium. This can section can be smaller if the pathology team needs to review more of the endometrium. The amount and location of removal of specimen is at the investigators clinical discretion. This should be snap frozen and shipped on dry ice.
- A portion of the formalin fixed paraffin embedded block, which was collected as standard of care per institutional pathology guidelines, will be sent to the University of Minnesota and cut into 10 unstained 5µm slides. If the FFPE block cannot be sent due to limited amount of tumor, then 10 unstained 5µm slides will be cut and the slides will be shipped to UMN. Blocks will be shipped on ice to prevent melting of the paraffin.

Historical matched controls from repository:

- Identify a list of potential matched controls from the repository for each site that will satisfy the matching criteria mentioned in section 3 of the protocol.
- For each matched control, two samples will be collected, first from the pre-surgical biopsy remnant tissue and the second from the surgical tissue. This tissue can be sent as a block or cut into 10 unstained 5µm slides.
- All blocks or slides will be shipped at the end of study.
- If slides are sent, they should NOT be cut until the time of shipment.

Tissue analysis will be performed at the University of Minnesota (UMN) as detailed below. Specimens from the University of Wisconsin and University of Alabama will be shipped by an overnight carrier to the Biorepository laboratory at the University of Minnesota:

Biorepository & Laboratory Services  
Attn: [name]  
[name]  
[name]  
[name]  
[name]

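### Section 8.2.4.3 promises a three-way ranking of tampon platforms for detecting disease; with no disease-free tampon group and no rule for a positive proteomic result, the design cannot deliver it

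*Combined protocol and SAP*

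**What the plan says.** The last sentence of Section 8.2.4.3 states, without qualification, that the design allows a "robust comparison of clinical utility between ultra-sensitive DNA sequencing, methylation analysis, and proteomics", and that this will "determine which platform is most sensitive for detection of disease".

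The sections that bear on whether it can are these.

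- **Who gives a tampon.** Section 4.1 requires "Females with a histologically proven CAH/ EIN or low grade (grade 1 or grade 2) endometrial carcinoma (EC) for which surgery is planned". Section 4 adds: "If the participant is either not eligible or refuses to sign the study consent, the tampon will be discarded". At the Italian site, Section 3 says "If CAH/EIN/low grade EC is confirmed then participants will sign the main study consent", and the first tampon is placed after that consent.
- **Historical controls.** They are matched on disease type (Section 3). Section 10.1.1 says that for each of them "two samples will be collected, first from the pre-surgical biopsy remnant tissue and the second from the surgical tissue". No tampon is involved.
- **Central review.** Section 13.1 expects some enrolled women not to have the disease on central review. Section 13.6 treats them as random loss and excludes them from analysis.
- **Proteomics.** Section 8.2.5 says: "For the proteomic pilot studies, we will analyze samples from the first 10 patients". On Olink and SomaLogic it says "it will not be possible to use either platform to analyze the protein extracts from the biopsies", and the same applies to tumour tissue. The extracts are kept for uses such as Western blot validation of proteins already identified in the tampon washings. An optional extension covers 30 further samples and may be restricted to women who responded.
- **Analysis.** Section 13.5 gives no positivity rule for any of the three platforms and no test that compares them.

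**The concern.** To rank tests by sensitivity, each must have a defined positive result, and the tests must be read at comparable false-positive rates, preferably in the same women. Sensitivity alone can be raised by loosening the cut-off, so without a shared false-positive rate the order of the platforms may reflect the cut-offs and not the assays.

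Here no group is planned from which a clinical false-positive rate could be estimated, one of the three platforms has no definition of a positive, and that platform may be run in fewer or selected women. At stake is a conclusion about detection that the data could not back. Section 8.2.5 expects the proteomic results from the tampon rinse to matter for later early-detection applications, so the claim should not exceed what the design can show.

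**Working it through.** The plan gives no sample size, precision or positivity rule for the platform comparison, so there is no figure of its own to reproduce.

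**1. Planned disease-free tampons.** Enrolled women: proven disease at entry. Ineligible women: tampon discarded. Historical controls: diseased, tissue only. Women without disease on central review: excluded. The planned comparison group is therefore 0. The last category may not be empty. Non-evaluable women are put at about 25%, so it holds at most 0.25 × 40 = 10, a number that also covers inadequate tissue.

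**2. What each platform is compared with.**

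| Platform | Reference for the tampon result | Positivity rule in Section 13.5 |
|---|---|---|
| Sequencing | Same woman's biopsy sequence (8.2.4.2) | None |
| Methylation array | Same woman's tumour on the same array (8.2.4.3) | None |
| Olink / SomaLogic | None on the same platform (8.2.5) | None |

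The proteomic contrasts in Section 8.2.5 are supernatant against pellet, before against after treatment, responder against non-responder, and CAH/EIN against cancer. None is disease against no disease.

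**3. Why a common false-positive rate matters.** Illustration with assumed binormal markers: d = √2 × Φ⁻¹(AUC), and sensitivity = 1 − Φ(Φ⁻¹(1 − FPR) − d).

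- AUC 0.65 read at a 50% false-positive rate: sensitivity 0.71.
- AUC 0.85 read at a 5% false-positive rate: sensitivity 0.43.
- AUC 0.65 read at 5%: sensitivity 0.14.

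At unequal false-positive rates the weaker marker ranks first (0.71 against 0.43). At the same 5% it ranks second (0.14 against 0.43).

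**4. Are the same women compared?** The proteomic pilot is 10 women × 4 samples = 40 samples. The extension is 30 samples of one type. If one sample per woman is used, that is up to 30 more women; if a before-and-after pair is used, it is 30 / 2 = 15. The text does not say which, and it allows restriction to responders.

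**5. Precision, supposing every platform had a valid positive/negative call.** Clopper-Pearson 95% limits for x of n are the 0.025 quantile of Beta(x, n − x + 1) and the 0.975 quantile of Beta(x + 1, n − x).

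- 8 of 10: 0.44 to 0.97.
- 7 of 10: 0.35 to 0.93.
- 21 of 30: 0.51 to 0.85.

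For a paired comparison, the exact two-sided McNemar p-value with m discordant women all in one direction is 2 × 0.5^m. Six give 2 × 0.5⁶ = 0.031 and five give 2 × 0.5⁵ = 0.063, so at least six are needed. Power, assuming the platform results are independent within a woman:

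| True sensitivities | n = 10 | n = 30 | n = 40 |
|---|---|---|---|
| 0.9 v 0.7 | 0.02 | 0.36 | 0.51 |
| 0.9 v 0.5 | 0.19 | 0.90 | 0.97 |

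For 0.9 v 0.7 the expected discordant share is 0.9 × 0.3 + 0.7 × 0.1 = 0.34, or 3.4 of 10 women, below the six required.

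**The case against.** The strongest reply is that sensitivity is by definition measured in diseased women, so controls are not needed. For part of the work this stands. Tampon variants are compared with those in the woman's own biopsy, with an anticipated detection limit of 0.01%, and tampon methylation is compared with her own tumour. Section 8.2.4.3 also pairs sensitivity with limit of detection, which is partly an analytical aim. A reader might infer that the tampon data can say nothing about detection, or that sequencing sensitivity could be set anywhere by choice of cut-off. The documents do not support that: matched-variant detection is tied to what was found in the tumour.

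A reader might also infer that every woman with a tampon truly has disease. Section 13.1 expects otherwise. Those women are excluded, and a positive referral biopsy would make them imperfect controls, so the accurate statement is that no disease-free comparison group is planned.

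Nor is proteomics cut off from tissue altogether. Western blots remain possible, and Sections 8.2.5 and 10.2.2 still speak of proteomics on the biopsies. But Western blots are offered as validation of proteins already seen in the tampon, and they do not create a rule for a positive result.

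The 10-woman figures apply to the proteomic pilot only. They do not describe sequencing against methylation, where up to about 30 evaluable women could contribute and a large difference (0.9 v 0.5) would be detectable under the stated assumptions.

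Finally, the disputed text is one rationale sentence. No listed objective or planned test ranks platforms. The tampon sequencing and proteomics are called exploratory, and Section 13.5 concedes that the study is not powered to identify all methylation markers. This limits the consequence, but the sentence still promises a definite result.

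**Conclusion.** The concern holds for the three-way ranking and the clinical-utility conclusion in Section 8.2.4.3. The design has no planned group for estimating a clinical false-positive rate, no rule for a positive proteomic result, and no assurance that the three platforms are run in the same women. It does not hold against tumour-matched detection by sequencing or tumour-tampon concordance by methylation, which remain estimable.

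The documents alone establish the missing group and the missing rules. The reversal of order rests on assumed binormal markers, and the McNemar power on assumed sensitivities and on independence within a woman. The interval of 44% to 97% for 8 of 10 needs only a valid positive/negative call. Severity is minor: the primary endpoint is unaffected.

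**What to change.** Replace the last sentence of Section 8.2.4.3, and add matching text to Section 13.5, as follows.

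- Report, as exploratory, the within-woman tumour-tampon detection rate for sequencing and the concordance for methylation, in women with both results. Fix the thresholds before tumour and tampon results are linked.
- Give each a chance-match rate from mismatched pairs: each tampon against other women's tumours, by permutation. State that those tumours are also diseased, so this is a baseline for agreement and not specificity in healthy women.
- Report proteomics descriptively. Make no ranking of platforms and drop the clinical-utility conclusion.
- Reconcile the statements that biopsies will undergo proteomics (Sections 8.2.5 and 10.2.2) with the later statement in Section 8.2.5 that Olink and SomaLogic cannot run those extracts.

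The cost is a less favourable claim, a wording change and one small permutation analysis on data already collected. No new samples are needed. Keeping the ranking instead would need disease-free tampons, a pre-set positivity rule for each platform, and a paired analysis in the same women.

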#### **8.2.5 Protein markers via tampon recovery before and after treatment:**

We propose a proteomic analysis of vaginal specimens and endometrial biopsies as an exploratory experiment to determine if response to exemestane correlates with a change in vaginal and endometrial proteins. Proteins identified in this experiment could potentially serve as surrogate biomarkers for exemestane response. We also anticipate discovering a different protein profile in the tampon collected proteins and tissue biopsies of women with CAH/EIN vs. low grade endometrial cancer.

[name] has successfully performed proteomic studies using the Olink platform on serum protein from healthy women and women with ovarian cancer. The methodology that [name] optimized in her preliminary studies will be applied to this study. The concentration of protein in each sample will be determined by using the bicinchoninic acid (BCA) assay. If necessary due to low protein yields in the tampon washings, they will be passed through an Amicon filter (3 kD cut-off) in order to concentrate the proteins. In preliminary studies, the total amount of protein in each 1 mL of tampon washing sample ranged from 65 to 500 ug (i.e. enough for multiple proteomic analyses). We also plan to extract protein from the

cell pellet that is saved from the tampon washing (described in 8.2.6.1) and from tumor biopsies (pre- and post-treatment with exemestane).

For the proteomic pilot studies, we will analyze samples from the first 10 patients that will be sent directly to the University of Minnesota. In particular, we will be analyzing 4 samples from each patient: (i) the PBS tampon washing pre-treatment, (ii) the cell pellet from the tampon washing pre-treatment, (iii) the PBS tampon washing post-treatment with exemestane, and (iv) the cell pellet from the tampon washing post-treatment with exemestane.

The rationale for using the PBS rinse of the tampon as well as the cell pellet from the tampon is four-fold.

1. The PBS rinse from the tampon is a rich source of protein that contains proteins that are secreted from the uterus (and endometrium), cervix, and vagina by the patient over the time period that the tampon was placed in her vagina. These proteins will be absorbed by the tampon (along with blood proteins and cells that are shed). In our previous studies, we found a sufficient amount of protein in the PBS rinse to perform protein based assays. .
2. The number of cells that are present in the cell pellet from the tampon may not be sufficient for us to perform the genomic studies and the proteomic studies. If the genomic study would take priority, then we would not have a sufficient amount of protein to conduct proteomics. Thus, we do not want to limit the proteomic portion of this study to just the cell pellet.
3. The proteins that are present in the PBS rinse may not be the same as those that are in the cell pellet. Thus, if were to limit this study to the identification of proteins present only in the cell pellet, we may miss proteins that could serve as candidate biomarkers for early stage endometrial cancer.
4. The proteomic results that we obtain from the PBS rinse will play a significant role in future applications for the detection of early stage endometrial cancer. In particular, we anticipate that women in the near future will be able to perform an at home self-administered vaginal swab, and then send the swab into a lab for proteomic detection of biomarkers for specific gynecological diseases. The PBS rinse is the closest we have come to this test becoming a reality.

We anticipate that the samples will contain varying amounts of blood, so we will use commercially available platforms that were specifically designed to be used with serum or plasma samples. There are currently two major companies that have products that would be amenable to the identification of protein biomarkers in serum samples: Olink and SomaLogic. Olink technology was initially designed to quantify the levels of proteins in sera and/or plasma using Proximity Extension Assays. (See their website at <https://www.olink.com/>) Thus, the Olink platform is well suited to handle the endometrial samples, which contain high amounts of blood proteins. The unique technology behind the Olink® Target 96 panels enables high-throughput, multiplex immunoassays that measure 92 proteins across 96 samples simultaneously using only one microliter of serum, or plasma. The Olink panels have also been used on other type of biological samples. We have searched their lists of more than 1500 proteins that they can measure in their 13 commercially available “Target 96” panels. We found >100 proteins that fall into the category of “proliferation” (which is the focus of this project) on five of their panels. Since each panel measures 92 proteins, this will result in generating data for the levels of  $92 \times 5 = 460$  proteins. This is far better than we could expect from MS experiments that are contaminated with blood proteins.

We propose to: 1-Determine the feasibility of using the Olink panels by running one panel (Immuno-Oncology) to analyze the tampon washing samples, since we are not certain of the dilution of protein that will yield optimal results. We will extract protein from the 20 tampon washing cell pellets and use various dilutions of the tampon washing cell pellet lysates and supernatants. We will place aliquots of the diluted samples into a 96-well microtiter plate from the 40 tampon washing samples (10 pre-treatment supernatants, 10 post-treatment supernatants, 10 pre-treatment cell pellets, and 10 post-treatment cell

pellets). We will provide these samples to the University of Minnesota Genomics Center, whose staff will run the samples as a fee-for-service. 1- send Olink ~50 ug of protein from the 40 tampon washing samples (10 pre-surgery supernatant, 10 post-surgery supernatant, 10 pre-surgery cell pellets, and 10 post-surgery cell pellets). 2- Once optimal dilutions have been determined, we will be able to test the other 4 Olink panels that are relevant to this study as a fee-for-service.

SomaLogic technology was also initially designed to quantify the levels of proteins in sera and/or plasma. However, SomaLogic uses technology based on aptamers to quantify protein levels in many types of samples (See their website at <https://somalogic.com/>). Their technology allows for the quantification of 7000 proteins simultaneously from 75 ul of protein at 0.2 ug/ul.

We propose to: 1- Send SomaLogic ~10 ug of protein from the 40 tampon washing samples (10 pre-treatment supernatants, 10 post-treatment supernatants, 10 pre-treatment cell pellets, and 10 post-treatment cell pellets). 2- As a fee-for-service, have SomaLogic run the 40 samples on their SomaScan platform.

Once we have the data back from Olink and SomaLogic, we will be able to analyze the data to identify proteins that are differentially expressed between the tampon supernatants and cell pellet lysates, the pre- and post-treatment samples from the same patient, as well as those proteins that are differentially expressed between the women whose tumors respond to Exemestane treatment and those whose tumors do not respond.

Since the Olink and SomaLogic platforms are not compatible with denatured proteins, it will not be possible to use either platform to analyze the protein extracts from the biopsies (which were extracted in AllPrep reagent for recovery of DNA and protein) or tumor tissues. The tissue sample extracts can be used for other protein experiments, such as validation of the proteins identified in the tampon washing samples by Western immunoblotting.

Option 3 of this project is to analyze a subset of the samples from the remaining 30 patients by proteomic techniques in a similar manner to those outlined above for Patients #1-10. In particular, based on the results that we obtain from the Proteomic Pilot study using 10 patients and 40 samples, we will be able to limit our next set of experiments to the one sample type (tampon washing or tampon cell pellet) that provided the best results, instead of analyzing all of the remaining 120 samples (i.e. 30 remaining patients x 4 samples each). For example, we would omit a sample type(s) that did not yield sufficient protein after removal of the highly abundant proteins. Or we may omit the sample type(s) that did not show any significant differences in proteins identified or quantified between the pre-treatment and the post-treatment. We may also decide to limit the samples to cases where the women responded to treatment. Thus, we will limit Option #3 to the analysis of an additional 30 samples. Thus, the cost of performing the experiments in Option #3 would cost the same as the experiments outlined in the Proteomic Pilot study. The data from these experiments will allow us to make comparisons between the sample sets and validate our results.

